7.12. Storage and analysis of clinical samples

Research samples including for NT-proBNP at baseline and 16 weeks and C-peptide at baseline will be stored locally and transferred to UoD, Division of Molecular and Clinical Medicine for analysis and storage either at the end of site participation or sooner if site requests.

Optional samples collected for future use will be stored locally and transferred to the UoD, Division of Molecular and Clinical Medicine either at the end of site participation or sooner if site requests. These samples will be registered with the Tayside Biorepository, part of the NHS Biorepository Network, and handled in accordance with the Human Tissue Act 2004 and the 2006 Human Tissue (Scotland) Act. The samples will remain under the control of the CI for use in future, ethically approved, research within the UoD and with other research collaborators (commercial and non-commercial). Access to the samples will be via application to the CI. Trial data may be released with samples as per section 7.2.1.

The collection, processing, storage and transfer of samples will be detailed in the Laboratory Manual. The analysis of samples will be detailed in the Laboratory Analytical Plans.

7.13. End of trial

The end of trial at all sites is defined as last participant last visit. The Sponsor, CI and/or the TSC have the right at any time to terminate the trial for clinical or administrative reasons.

The end of the trial will be reported to the Sponsor, Research Ethics Committee (REC) Medicines and Healthcare products Regulatory Agency (MHRA) and National Health Service Research & Development (NHS R&D) Office(s) within 90 days, or 15 days if the trial is terminated prematurely. The PI will be responsible for arranging any appropriate follow-up for their participants.

A final clinical trial report will be published and the MHRA informed within 1 year of the end of the trial and will also be provided to the Sponsor and REC.

8. TRIAL TREATMENTS

8.1. Name and description of investigational medicinal product(s)

IMP	Dosage, form and strength	Placebo	Dosage, form and strength
Sotagliflozin	200mg oral tablet	matched	200mg oral tablet

8.2. Regulatory status of the drug

Sotagliflozin was approved for use in the UK by NICE at a dose of 200mg once daily in individuals with type 1 diabetes, BMI $\geq 27\text{kg/m}^2$ and taking insulin dose ≥ 0.5 units/kg body weight (Technology Appraisal TA622).

Sotagliflozin does not have a marketing Authorisation in the UK.

Sotagliflozin (Inpefa) was recently approved for use in the United States of America by the Food and Drug Administration in all patients with HF without limitations on use in individuals with type 1 diabetes.

8.3. Product Characteristics

The reference safety information (RSI) is described in Section 9.4.

8.4. Preparation and labelling of Investigational Medicinal Product

IMP and placebo tablets will be supplied to Clinical Trial Pharmacies in bottles labelled with annex 13 compliant labels. Bottles will be fitted with child-proof caps. Further details will be provided in the Pharmacy Manual.

8.5. Drug storage and supply

Trial drug will be stored at each site's Pharmacy/Clinical Trials Pharmacy securely between 15°C and 30°C, away from direct sunlight. Further details will be provided in the Pharmacy Manual.

8.6. Accountability Procedures

All IMP will be supplied by Lexicon Pharmaceuticals and labelled, Qualified Person released and distributed to sites by Sharp Clinical Services. Trial drug will be received by a delegated person at the trial site Clinical Trial Pharmacy, handled and stored safely and properly, and kept in a secured location as detailed in the Pharmacy Manual. All trial clinical supplies will be dispensed only in accordance with the protocol and Pharmacy Manual.

The PI or delegated trial staff will maintain an accurate record of the receipt and dispensing of the IMP. Monitoring of drug accountability will be performed as per Sponsor Monitoring Plan.

8.7. Dosage schedules

Participants will take one 200mg tablet of Sotagliflozin/matched placebo daily for a total of 16 weeks, usually before breakfast. If the participant misses a dose of the trial drug by less than 6 hours, they should still take it when remembered and then continue all subsequent doses as scheduled. If a participant misses a dose by more than 6 hours after it was scheduled then they should skip that dose and only take their next dose at their next scheduled time (i.e. the next day before breakfast).

8.8. Dosage modifications

No routine dose modification is planned during the trial. Participants will remain on a single dose of sotagliflozin 200mg daily or matched placebo throughout the trial.

8.9. Known drug reactions and interaction with other therapies

Insulin: may increase the risk of hypoglycaemia, see section 7.8 for mitigation of risk and insulin dose adjustments.

UGT enzyme inducers e.g. phenytoin, ritonavir, rifampicin: may decrease efficacy of sotagliflozin. Blood glucose management will be reviewed at each visit.

Digoxin: increase in AUC_{0-mf} and C_{max} of digoxin. If digoxin toxicity is clinically suspected appropriate clinical action will be taken. This is likely to include checking digoxin levels.

Sotagliflozin may increase exposure of rosuvastatin, fexofenadine, paclitaxel, bosentan, methotrexate, furosemide, benzylpenicillin. It should be evaluated if additional safety monitoring is needed.

CYP2C9, CYP2B6 and CYP1A2: substrates of these enzymes should be monitored for decreases in their efficacy.

8.10. Concomitant medication

Details of all concomitant medications will be recorded on the trial eCRF on a concomitant medications log.

Other SGLT2 inhibitors are not permitted during the trial.

8.11. Trial restrictions

Patients should not be on a ketogenic diet.

WOCBP must be willing to have pregnancy testing prior to trial entry and prior to start of trial drug.

A woman is considered of childbearing potential, i.e. fertile, following menarche and until becoming post-menopausal unless permanently sterile. A post-menopausal state is defined as no menses for 12 months without an alternative medical cause (including use of hormone replacement therapy).

In addition, WOCBP must be willing to use a form of a medically approved birth control method throughout the trial (and for minimum of 16 weeks after last dose), which include:

- combined (oestrogen and progestogen containing) hormonal contraception associated with inhibition of ovulation:
 - oral
 - intravaginal
 - transdermal
- progestogen-only hormonal contraception associated with inhibition of ovulation
 - oral
 - injectable
 - implantable
- intrauterine device (IUD)
- intrauterine hormone-releasing system (IUS)
- bilateral tubal occlusion
- vasectomised partner
- male condom
- sexual abstinence, when this is in line with the preferred and usual lifestyle of the participant, abstinence is acceptable only as true abstinence. Periodic abstinence (e.g. calendar, ovulation, symptom-thermal, post-ovulation methods) and withdrawal are not acceptable methods of contraception.

Men who are sexually active with WOCBP will also be required to use a form of medically approved birth control method as listed above throughout the trial (and for minimum of 16 weeks after last dose) and will be requested to inform the trial team of any pregnancy occurring.

8.12. Assessment of compliance with treatment

Adherence to trial drug will be checked by tablet counting at visit 7. Participants will also be asked at each visit regarding their adherence to taking the trial drug daily.

9. PHARMACOVIGILANCE

9.1. Definitions

Term	Definition
Adverse Event (AE)	Any untoward medical occurrence in a consented participant which is not necessarily caused by or related to a medicinal product.
Adverse Reaction (AR)	
An untoward and unintended response in a participant to an IMP which is related to any dose administered to that participant.
 
The phrase "response to an IMP" means that a causal relationship between a trial drug and an AE is at least a reasonable possibility, i.e. the relationship cannot be ruled out.
 
All cases judged by either the reporting medically qualified professional or the Sponsor as having a reasonable suspected causal relationship to the trial drug qualify as adverse reactions. It is important to note that this is entirely separate to the known side effects listed in the summary of product characteristics (SmPC). It is specifically a temporal relationship between taking the drug, the half-life, and the time of the event or any valid alternative aetiology that would explain the event.
 
Assessment of severity of AR:
 
Mild: A reaction that is easily tolerated by the trial participant, causing minimal discomfort, and not interfering with everyday activities.
 
Moderate: A reaction that is sufficiently discomforting to interfere with normal everyday activities and may warrant intervention.
 
Severe: A reaction that prevents normal everyday activities or significantly affects clinical status and usually warrants intervention.

Serious Adverse Event (SAE)	
A serious adverse event is any untoward medical occurrence that:
 
 • results in death • is life-threatening • requires inpatient hospitalisation or prolongation of existing hospitalisation • results in persistent or significant disability/incapacity • consists of a congenital anomaly or birth defect 
Other 'important medical events' may also be considered serious if they jeopardise the participant or require an intervention to prevent one of the above consequences.

	NOTE: The term "life-threatening" in the definition of "serious" refers to an event in which the participant was at risk of death at the time of the event; it does not refer to an event which hypothetically might have caused death if it were more severe.
Serious Adverse Reaction (SAR)	An adverse event that is both serious and, in the opinion of the reporting Investigator, believed with reasonable probability to be due to one of the trial treatments, based on the information provided.
Suspected Unexpected Serious Adverse Reaction (SUSAR)	A serious adverse reaction, the nature and severity of which is not consistent with the information about the medicinal product in question set out in the reference safety information: 
 in the case of a product with a marketing authorisation, this could be in the SmPC for that product, so long as it is being used within its licence. If it is being used off label an assessment of the SmPCs suitability will need to be undertaken. in the case of any other IMP, in the investigator's brochure (IB) relating to the trial in question

NB: to avoid confusion or misunderstanding of the difference between the terms "serious" and "severe", the following note of clarification is provided: "Severe" is often used to describe intensity of a specific event, which may be of relatively minor medical significance. "Seriousness" is the regulatory definition supplied above.

Causality assessment

Unrelated	Where the AE is not considered to be related to the trial drug.
Possibly	Although a relationship to the trial drug cannot be completely ruled out, the nature of the event, the underlying disease, concomitant medication, or temporal relationship make other explanations more likely. Information on drug withdrawal may be lacking or unclear.
Probably	The temporal relationship and absence of a more likely explanation suggest the event could be related to the trial drug. Information on drug withdrawal may be available and if so the observed response to trial drug withdrawal is considered clinically reasonable
Definitely	The known effects of the trial drug or its therapeutic class, or based on challenge testing, suggest that the trial drug is the most likely cause. Information on drug withdrawal is usually available and the observed response to trial drug withdrawal is considered clinically reasonable and has a plausible temporal relationship to trial drug exposure

9.2. Operational definitions for (S)AEs

Worsening of glycaemic control, including hypoglycaemia and DKA during the trial will not be classed as an AE but are defined as outcomes. However, any events requiring hospitalisation or resulting in death, will be recorded as AEs and classified as SAEs.

Clinically significant volume depletion (as judged by the local investigator) or intercurrent illness requiring a temporary cessation of study drug will be recorded as an AE.

An abnormal laboratory finding, that requires medical intervention by the investigator, or a finding judged by the investigator as medically significant, will be reported as an AE. If clinical sequelae are associated with a laboratory abnormality, the diagnosis or medical condition will be reported (e.g. renal failure, haematuria) not the laboratory abnormality. Abnormal laboratory values that are not, in the investigator's opinion, medically significant and do not require intervention will not be reported as AEs

A non-clinically significant, in the opinion of the investigator, worsening of a pre-existing condition during the trial will not be classed as an AE. Pre-specified elective hospitalisations for treatment planned prior to randomisation will not be considered as an AE. However, any AEs occurring during such hospitalisations will be recorded.

9.3. Recording and reporting of SAEs, SARs AND SUSARs

All AEs will be recorded on the AE Log in the eCRF. Details of AEs will be recorded in the participant's medical record. AEs will be assessed for severity and causality by the PI or delegate. AEs will be recorded from the time a participant consents to join the trial until the participant's last trial visit. Any SUSAR, that the investigator becomes aware of, will be reported to the Sponsor irrespective of how long after trial treatment administration the reaction has occurred.

Assessment of severity:

Mild: An event that is easily tolerated by the trial participant, causing minimal discomfort, and not interfering with everyday activities.

Moderate: An event that is sufficiently discomforting to interfere with normal everyday activities and may warrant intervention.

Severe: An event that prevents normal everyday activities or significantly affects clinical status and usually warrants intervention.

An AE may be classified as a SAE or AR.

Participants with unresolved AEs/SAEs at end of trial will be followed up until 30 days after participant's last visit. SUSARS will be followed until resolution, where a participant agrees to this.

The CI, PI or delegate will ask about the occurrence of AEs and hospitalisations at every visit during the trial. SAEs will be submitted to the Sponsor Pharmacovigilance Section via the online Tayside Pharmacovigilance System within 24 hours of becoming aware of the SAE. Site PIs will also notify the CI when submitting an SAE.

The evaluation of expectedness will be made based on the knowledge of the reaction and the relevant safety information (RSI) see Section 9.4. The Sponsor will make the assessment on expectedness.

The Sponsor is responsible for reporting SUSARs to the MHRA and the REC. Fatal or life-threatening SUSARs will be reported within 7 days and non-fatal and non-life threatening SUSARs within 15 days.

Reporting of safety data to the funders will be as detailed in the funding agreement.

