3.2. Table of endpoints/outcomes

Primary Objective		
Objectives	Outcome Measures	Timepoint(s)
To investigate the effect of sotagliflozin 200mg once daily in addition to standard of care on quality of life	Change from baseline in KCCQ clinical summary score	Weeks 0 and 16

Secondary Objectives		
Objectives	Outcome Measures	Timepoint(s)
To investigate the effect of sotagliflozin 200mg once daily in addition to standard of care on QoL	Change from baseline in KCCQ clinical summary score	Weeks 0 and 4
	Change from baseline in KCCQ overall summary score	Weeks 0, 4 and 16
	Proportion of participants with a ≥ 5 , ≥ 10 and ≥ 15 point increase in KCCQ clinical and overall summary scores	Weeks 0 and 16
	Change from baseline in Diabetes Treatment Satisfaction Questionnaire (DTSQs and DTSQc)	Weeks 0 and 16
	Change from baseline in EQ-5D-5L score	Weeks 0 and 16
To investigate the effect of sotagliflozin 200mg once daily in addition to standard of care on walking distance	Change from baseline in distance covered during 6-minute walk test	Weeks 0 and 16
To investigate the effect of sotagliflozin 200mg once daily in addition to standard of care on NT-proBNP	Change from baseline in NT-proBNP	Weeks 0 and 16
To investigate the effect of sotagliflozin 200mg once daily in addition to standard of care on glycaemic control	Change from screening in HbA1c	Screening and week 16

To provide information on safety and tolerability of sotagliflozin 200mg once daily in addition to standard of care compared to placebo	Proportion of participants with level 2 or level 3 hypoglycaemia	Week 0 to weeks 16 and 20
	Proportion of participants with DKA	Week 0 to weeks 16 and 20
	Proportion of participants requiring hospitalisation due to HF	

Exploratory Objectives		
Objectives	Outcome Measures	Timepoint(s)
To investigate the effect of sotagliflozin 200mg once daily in addition to standard of care on HF symptoms, signs and clinical outcomes	Change from screening in New York Heart Association (NYHA) class	Screening, weeks 16 and 20
	Change from baseline in daily loop diuretic dose	Weeks 0 and 16
	Change from baseline in systolic and diastolic blood pressure.	Weeks 0 and 16
	Number of hospitalizations and deaths (first and total number) due to heart failure	Week 0 to weeks 16 and 20
To investigate the effect of sotagliflozin 200mg once daily in addition to standard of care on renal parameters	Change from baseline in eGFR, serum creatinine, urine albumin to creatinine ratio	Weeks 0 and 16

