7.7. Trial assessments

- Trial assessments will be performed according to the Schedule of Procedures, Appendix 4. Where trial assessments identify any clinically significant incidental findings, these will be communicated to the participant's GP, with the participant's consent.

Trial assessments will be carried out according to trial specific processes described in training documents.

Missed trial assessments or visits completed outside the visit window will not be reported as breaches where this is due to participant choice or a clinical decision. Excursions will be documented, and trial statistician made aware of discrepancies.

Demographics: Age, sex at birth, ethnicity.

Medical history: Focused medical history, taken from medical records and participant reporting, including the following information:

- Medical history required to confirm eligibility.
- History and diagnosis of HF including aetiology, if known.
- History and diagnosis of diabetes and diabetes-related complications including previous ketoacidosis, severe hypoglycaemia and microvascular complications (retinopathy, nephropathy and neuropathy).
- History of chronic medical conditions related to inclusion and exclusion criteria.
- Medication allergies.

Review of concomitant medications and therapies: taken from medical records and participant reporting. Participants are expected to be on optimal heart failure therapy as judged by their treating clinician and remain on stable doses of these throughout the duration of the trial.

NYHA class:

- I No limitation of physical activity. Ordinary physical activity does not cause undue fatigue, palpitations, or dyspnoea (shortness of breath).
- II Slight limitation of physical activity. Comfortable at rest. Ordinary physical activity results in fatigue, palpitations, or dyspnoea (shortness of breath).
- III Marked limitation of physical activity. Comfortable at rest. Less than ordinary activity causes fatigue, palpitations, or dyspnoea.
- IV Unable to carry on any physical activity without discomfort. Symptoms of HF at rest. If any physical activity is undertaken, discomfort increases.

Review of adverse events (AE): participants will be asked about the occurrence of any AEs since the previous visit. Medical records will also be reviewed.

Height, weight, waist circumference and hip circumference.

Blood Pressure and pulse: seated recording.

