10. STATISTICS AND DATA ANALYSIS

10.1. Sample size calculation

The sample size calculation was informed by the recent DEFINE-HF³¹ trial of dapagliflozin vs. placebo in participants with symptomatic HF with reduced ejection fraction and type 2 diabetes or no diabetes, in which dapagliflozin caused an improvement of 4.7 points in the KCCQ Clinical Summary Score (SD 13.7) compared to placebo. To achieve 80% power to identify this difference at an alpha of 0.05, 268 participants (134/group) are required. Accepting the potentially greater attrition in a type 1 diabetes population a ~15% trial dropout will be allowed for and therefore it is planned to recruit 320 individuals. An improvement of ~5 points in KCCQ is accepted as a clinically important difference²⁹ and is certainly consistent with that seen in SGLT2i HF trials (Table 2), for example PRESERVED-HF³², in which individuals with HFpEF were recruited and the magnitude of improvement in KCCQ was even larger than in DEFINE-HF (5.8 points). The KCCQ Clinical Summary Score is accepted for use in regulatory submissions to the FDA.

CMR sub-study sample size calculation

A recent study found that dapagliflozin caused a 50% increase in myocardial flow reserve measured using PET/CT.⁴⁴ In a predominantly non-diabetic cohort a 1SD increase in stress MBF (0.71 mL/g/min) was associated with a 54% relative risk reduction in MACE after a median of 20 months⁴⁷, while CMR-derived MPR is ~20% lower in T1D than in controls⁴⁸, so it is hypothesised that changes of these magnitudes in stress MBF and/or MPR could be clinically meaningful. To have 90% power to detect a 0.71 mL/g/min in stress MBF between sotagliflozin and placebo groups 44 participants are required, assuming balance in randomisation (22 per group).

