10.5. Participant population

The primary analysis will be by intention to treat (ITT), defined as all participants successfully randomised. Sensitivity analyses using both modified ITT (all randomised participants with at least one evaluable endpoint) and per-protocol data will also be performed.

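### Sections 9.3 and 7.11 give no way to record hospitalised events once a participant stops visits, although the DKA, hypoglycaemia and HF hospitalisation outcomes run to week 20

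*Protocol*

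**What the plan says.** **Outcome windows.** Section 3.2 lists "Proportion of participants with DKA" and the proportion with level 2 or 3 hypoglycaemia as secondary safety outcomes, with the window "Week 0 to weeks 16 and 20". The exploratory count of hospitalisations and deaths due to heart failure has the same window.

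**Which rule covers which event.** Section 9.2 states: "Worsening of glycaemic control, including hypoglycaemia and DKA during the trial will not be classed as an AE but are defined as outcomes". It then adds: "However, any events requiring hospitalisation or resulting in death, will be recorded as AEs and classified as SAEs". Hospitalised or fatal DKA and hypoglycaemia are thus also AEs and SAEs. An HF admission is an SAE under the definition in section 9.1.

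**Recording period.** Section 9.3 states: "AEs will be recorded from the time a participant consents to join the trial until the participant's last trial visit".

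**How events are found.** Under section 7.7, participants are asked about AEs since the previous visit, and "Medical records will also be reviewed". Section 9.3 has AEs and hospitalisations asked about at every visit. Appendix 5 places record review and questioning at all visits. Appendix 4 marks the AE row, and the separate row for hypoglycaemic and DKA events, at visits 2 to 8.

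**Withdrawal.** Section 7.11 asks withdrawn participants who have taken trial drug to complete the visits, but they may refuse. Section 7.11.1 encourages those who stop the drug to complete all visits and calls.

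**Expected loss.** Section 10.1 states: "Accepting the potentially greater attrition in a type 1 diabetes population a ~15% trial dropout will be allowed for".

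**The concern.** The outcomes are defined to a fixed date, but the means of finding events lasts only as long as the participant keeps attending. A person who declines visits after week 4 can be admitted with heart failure or DKA at week 10, and no step in the protocol requires the site to look. The hospital record would show the admission, and sites already consult that record, but only in connection with a visit.

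These are infrequent events that serve a stated safety objective, and the decision to stop attending may be related to them. An event that is never collected cannot be recovered by any missing-data method specified later.

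**Working it through.** **1. Number of participants concerned.** Inputs from section 10.1: 268 evaluable, about 15% dropout, 320 recruited.
- The plan's own inflation: 268 / (1 − 0.15) = 315.3, so 316. The stated 320 is slightly more generous (1 − 268/320 = 16.25%).
- Leavers at the planned rate: 320 × 0.15 = 48. This is an upper figure for the gap, because some of those who miss the primary endpoint may still attend or take calls.

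**2. Route of ascertainment, by event and by whether visits continue.**

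| Event | Governing text | Visits continue to week 20 | Visits refused |
|---|---|---|---|
| HF hospitalisation | 9.1, 9.3 (SAE) | Covered | No active route |
| Hospitalised DKA or level 3 hypoglycaemia | 9.2, 9.3 (SAE), and own row in Appendix 4 | Covered | No active route; the Appendix 4 row is also completed at visits |
| DKA or hypoglycaemia without admission | 9.2 (outcome, not AE), own row in Appendix 4 | Covered | No active route, and hospital records would mostly not show it |
| Death | 9.6 | Covered | Largely covered: all deaths during the trial are reportable |

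For a participant who completes the trial, the last trial visit is visit 8 at week 20, so the whole window is covered. The gap exists only for those who stop attending.

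**3. The wording of 9.3 for a leaver.** The participant's last trial visit can mean the last one attended or the scheduled visit 8. On the first reading, recording stops early. On the second, recording nominally continues, but 7.7, 7.11 and the appendices supply no means of doing it. Both readings leave the same practical gap.

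**4. Why no effect on the results is claimed.** As an illustration only, take the DKA risks that section 2.1 cites from another programme (2.7% and 0.5%, with no follow-up period given). Assume a constant event rate, a share d of each arm leaving, leavers observed for a fraction f of the window, and all randomised participants in the denominator. The protocol adopts none of these assumptions. The observed risk is p × [1 − d(1 − f)].
- Complete follow-up: 2.7 / 0.5 = 5.4; difference 2.2 points.
- d = 15% in both arms, f from 0 to 0.5: the bracket is 0.85 to 0.925 in both arms and cancels. The ratio stays 5.4 and the difference is 1.87 to 2.04 points.
- d = 20% active and 10% placebo (assumed): f = 0 gives 2.16 / 0.45 = 4.8; f = 0.5 gives 2.43 / 0.475 = 5.1.
- The reverse split (assumed): 5.7 to 6.1.

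The direction and size depend on how dropout differs by arm, which the protocol does not give.

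**The case against.** The strongest reply is that 9.3 is an AE rule, while DKA and hypoglycaemia are outcomes with their own collection row to week 20. That is right for events without admission. It does not dispose of the point, because 9.2 brings admitted cases back under the AE and SAE rule, and the separate row also depends on visits.

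Second, the protocol works to keep people in. Stopping the drug is separate from leaving, withdrawn participants are asked to continue, and visits 4, 6 and 8 may be remote. SAEs are reportable within 24 hours of awareness, and SUSARs without time limit. All of this stands and will shrink the number affected. It does not help when a participant refuses every contact and the site has no prompt to look. The protocol does make such a distinction for participants who lose capacity: section 7.2 allows data collection to be agreed after withdrawal from clinical intervention. Ordinary withdrawals have no equivalent.

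Third, a reader might infer that leavers will be counted as event-free for the unobserved weeks. The documents do not support this. Section 10.5 says "The primary analysis will be by intention to treat (ITT), defined as all participants successfully randomised", which concerns the primary analysis. No section fixes the denominator of the safety proportions, and section 10.3 leaves the participant population and missing data to the SAP. A reader might also be tempted to state a share of person-time lost or a number of missed DKA cases. That would need an assumed pattern of departure and a DKA rate borrowed from another programme.

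**Conclusion.** The point holds as a low-cost improvement to data collection. For leavers, up to about 48 of 320 if the planned 15% is reached and all of them decline contact, the protocol has no active way to find HF hospitalisations or hospitalised DKA and level 3 hypoglycaemia between the last visit and week 20. The number of events lost cannot be derived from the protocol. With equal dropout and equal observed time in both arms the DKA risk ratio would not change, and only the absolute risks would be understated if leavers stayed in the denominator. Bias between arms would require dropout that differs by arm or is related to the event; this is possible but not shown. The primary KCCQ analysis and its sample size are unaffected.

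**What to change.** In section 9.3, state that SAEs, hospitalised DKA, hospitalised level 3 hypoglycaemia and HF hospitalisation are recorded to the participant's scheduled week-20 date whether or not visits are attended. This also removes the ambiguity in the present wording.

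In section 7.11 and the participant information, separate stopping visits from refusing access to medical records. For those who only stop visits, have the site check the medical record at the scheduled week-16 and week-20 dates and enter any such event in the eCRF.

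The cost is an amendment, a short addition to the participant information, and at most 2 × 48 = 96 record checks. Events managed without hospital contact, such as level 2 hypoglycaemia, would still be missed in these participants. The change helps only those who leave after it is in place, so it should be made soon.
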